#### *Antibiotic use*

Records on concomitant medications will be searched for use of any of the following drugs during the 28-day follow up period: ampicillin, amoxicillin/amox, septrin (cotrimoxazole), flagyl (metronidazole), gentamicin/gentamycin, ciprofloxacin, cloxacillin, cephalosporin (ceftriaxone, cephalexin), ampiclox, augmentin/co-amoxiclav, penicillin, chloramphenicol, erythromycin.

Because tetracycline and chloramphenicol are given prophylactically at birth as part of routine care, we will exclude these records from this outcome.

#### *Bacterial carriage*

Swabs will be tested for particular bacteria as outlined in Table 4. Each swab will be classified as positive or negative for each bacteria.

**Table 4** Bacteria isolated from each swab type collected in infants

Swab	Samples collected	Bacteria
NPS	day 0, day 6, day 28, 4 months	S. pneumoniae and Klebsiella
Rectal	day 0, day 6, day 28, 4 months	E. coli and Pseudomonas , Klebsiella
OPS	day 0, day 6, day 28, 4 months	S. aureus , GBS and GAS

#### **Secondary endpoints – mother**

##### *Post-partum sepsis*

A case will be recorded if either:

$\geq 2$  of the following criteria are recorded during an admission:

i) uterine tenderness, ii) foul smelling lochia, iii) abnormal vaginal discharge iv) temperature  $\geq 38^{\circ}C$ .

OR

$\geq 2$  of the above criteria are recorded at an OPD visit and the mother is admitted within 24 hours of the visit

OR

The mother is diagnosed with post-partum sepsis at admission AND 1 of the above clinical criteria is recorded

The case will be considered culture-confirmed if, in addition, a positive CSF, blood, or wound culture is recorded.

#### *Clinical Mastitis*

A case will be recorded if “Breast pain/Engorgement” or “mastitis” is recorded on an admission, unsolicited AE, or on an OPD form or solicited AE (day 28) form. The case will be classified as culture-confirmed if it is associated with a culture-positive breast swab.

#### *Malaria*

A mother will be considered positive for malaria parasitaemia if she tests positive by microscopy or rapid diagnostic test during a hospital admission or OPD visit.

#### *Antibiotic use*

Records on concomitant medications will be used to identify maternal antibiotic use (see definition of antibiotic use in neonate for the (non-exhaustive) list).

#### *Fever*

A case of fever will be recorded if an axillary temperature  $\geq 38.0$  °C, not attributable to external warming, is recorded in the mother during an admission or OPD visit.

#### *Bacterial carriage*

Swabs will be tested for particular bacteria as outlined in Table 5. Each swab will be classified as positive or negative for each bacteria.

**Table 5** Bacteria isolated from each swab type collected in mothers

Swab	Sampling times	Bacteria
NPS	day 0*, day 6	E. coli , S. pneumoniae and Klebsiella spp
Recto-vaginal swab	day 0*	E. coli and Pseudomonas , Klebsiella
OPS	day 0*, day 6	S. aureus , GBS and GAS

Breast milk	day 6, day 28, 4 months	S. aureus , GBS, GAS, E. coli , Pseudomonas and Klebsiella
-------------	-------------------------	-------------------------------------------------------------------------------------------

\*Samples collected before treatment. The samples may have been collected on day -1 rather than day 0.

## 5 Sample Size

(ICH E3; 9.7.2. ICH E9; 3.5)

The study was originally designed to assess the effect of the intervention on mortality. We assumed mortality in the placebo arm would be at least 1.4% and that the intervention would reduce mortality by 40%. Based on these parameter values, and allowing for 8% loss to follow-up, it was estimated that a total of 12,500 women would need to be recruited to achieve 80% power to detect such an effect.

However, during the course of the study data from the MORDOR study was published (Keenan et al., 2018) which suggested that the intervention was unlikely to achieve a 40% reduction. Study power was also negatively impacted by the lower than anticipated incidence of mortality (the observed mortality up to Jan 2020 was lower than anticipated (0.7%) probably because of the improved care associated with participating in the trial), and by the recruitment freeze between March and August 2020, which resulted in the target sample size being reduced from 12,500 to 12,000.

Because of this loss of study power, we decided to change the primary outcome from neonatal mortality to the composite endpoint of neonatal mortality + neonatal Sepsis. The revised power calculations are shown in Table 6. The calculations are based on mortality and sepsis data collected up to the end of Jan 2020 and effect size of 25% (RR=0.75) for mortality and 30% (RR=0.70) for sepsis. The revised study power is 82% power.

**Table 6** Revised study power calculation

Gambia parameters		Gambia	Control	AZI	Power
Total N	7000	N	3500	3500	
Incidence sepsis	1.9%	Sepsis	2.2%	1.6%	0.54
Incidence mortality	0.7%	Mortality	0.8%	0.6%	0.17
Proportion deaths due to sepsis	31%	Combined	2.8%	2.0%	0.60

### **Burkina Faso parameters**

### **Burkina Faso**

Total N	5000	N	2500	2500	
Incidence sepsis	1.8%	Sepsis	2.1%	1.5%	0.39
Incidence mortality	0.7%	Mortality	0.8%	0.6%	0.13
Proportion deaths due to sepsis	17%	Combined	2.8%	2.0%	0.46
RR sepsis	0.7	Overall			
RR mortality	0.75	N	6000	6000	
		Sepsis	2.2%	1.5%	0.76
Significance level (z-value)	1.96	Mortality	0.8%	0.6%	0.26
		Combined	2.8%	2.0%	0.82

## 6 General Considerations

### 6.1 Timing of Analyses

The final analysis of the primary endpoint will be performed when the recruitment target has been reached, and data up to day 28 has been entered into the main database (see data management plan) and verified for all participants.

### 6.2 Analysis Populations

(ICH E3; 9.7.1, 11.4.2.5. ICH E9; 5.2)

#### Primary analysis cohort

The cohort will include all mother–newborn dyads (or triads in the case of twins) who have been randomised to one of the study arms and where the day–28 survival status is known for all members of the dyad/triad. Dyads/triads where the survival status of all members cannot be determined from the day 28 visit or previous death records, or who have withdrawn from the study, will be excluded from the cohort.

We do not anticipate significant non–compliance and therefore do not intend to conduct a per protocol analysis. In the unlikely event that >10% of the study women do not ingest the study pills then we will conduct an additional analysis of the primary outcome restricted to mother–newborn dyads/triads where the mother is known to have ingested the medication.

Each subject’s inclusion or exclusion status in the primary analysis population will be assigned prior to breaking the code.

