### **Anthropometric cohort**

The cohort will include all infants who meet the following criteria:

- Selected to be in the anthropometric cohort
- Included in the primary analysis cohort
- Alive and participating in the study at day 28

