## 8 Efficacy Analyses

### 8.1 Primary analysis cohort

#### Primary outcome

We will report the proportion that meet the criteria for the primary outcome (death or sepsis within 28 days of birth) in each arm.

The null hypothesis of no difference between the arms will be tested by fitting a logistic regression model that, in addition to study arm, includes 1-minute Apgar score and birthweight as continuous, linear covariates. The p-value, odds ratio and

confidence interval associated with study arm will be reported, with the confidence interval and p-value being based on a Wald test.

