### **Mortality and sepsis**

Mortality and sepsis will be analysed separately, as secondary outcomes, as well as being part of the primary outcome.

They will be analysed as binary outcomes and as time to event outcomes using Kaplan Meier curves. In the K-M analysis of sepsis, death will be treated as a censoring event. There will be no censoring in the analysis of mortality because any neonate whose day 28 survival status is unknown is excluded from the Primary cohort.

A concern in the analysis of composite endpoints is that of competing risks. In this analysis, death is a competing risk for sepsis – an individual who has died is not at risk of sepsis. Although some bias due to the competing risk of death is expected in the K-M analysis of sepsis, the bias will be small because death is a rare outcome.

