### **Secondary outcomes**

The secondary outcomes are all binary and will therefore be analysed using logistic regression as described for the primary outcome (except the specific aetiologies of sepsis which will be analysed using Fisher's exact test because these are rare outcomes).

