### 8.3 Anthropometric cohort

Standardised anthropometric Z-scores (WHZ, WAZ, HAZ and MUAC-for-age, head-circumference-for-age) based on WHO 2006 growth charts will be calculated using the Stata package “zanthro” (Vidmar et al., 2013).

As recommended in the WHO report on data quality in anthropometric studies

<https://www.who.int/nutrition/publications/anthropometry-data-quality-report-chapter3.pdf>, a flag system will be used to recode implausible z-score values as missing:

- height-for-age:  $< -6$  or  $> +6$
- weight-for-length/height:  $< -5$  or  $> +5$
- weight-for-age:  $< -6$  or  $> +5$

- body mass index-for-age:  $< -5$  or  $> +5$

For each anthropometric measure, we will compare between study arms the mean score at 6 months, 12 months, and growth velocity, i.e. difference between 6 and 12-month scores. Linear regression will be used to calculate a difference between arms and p-value adjusted for country, birth weight and 1-minute Apgar score. The continuous variables (birth weight and Apgar score) will be included in the model as linear terms.

In addition, we will dichotomise the Z-scores using  $< -2$  SD as the cut-off for malnutrition and  $< -3$  SD as the cut-off for severe malnutrition. We will use logistic regression to adjust for country, birth weight and 1-minute Apgar score.

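### Twins share a mother and an allocation, but the newborn models appear to treat them as independent; intervals are slightly too narrow and p-values slightly too small

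*SAP*

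**What the plan says.** SAP section 6.2, Primary analysis cohort, defines the population by randomised mother with her newborn or newborns: "or triads in the case of twins) who have been randomised to one of the study arms". Section 4.1 and the carriage cohort definition in section 6.2 also keep twins, as triads.

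Section 8.1 tests the primary outcome with a logistic model that, besides study arm, "includes 1-minute Apgar score and birthweight as continuous, linear covariates", "with the confidence interval and p-value being based on a Wald test". The binary secondary outcomes "will therefore be analysed using logistic regression as described for the primary outcome", except for specific aetiologies of sepsis, which go to Fisher's exact test. Under Mortality and sepsis, section 8.1 says that "any neonate whose day 28 survival status is unknown is excluded from the Primary cohort".

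The anthropometric cohort in section 6.2 is defined by infant: "The cohort will include all infants who meet the following criteria". Section 8.3 then says: "Linear regression will be used to calculate a difference between arms and p-value adjusted for country, birth weight and 1-minute Apgar score".

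Nowhere does the SAP mention a variance clustered on mother, generalised estimating equations (GEE), a random effect, a rule for choosing one twin, or a rule for counting an outcome once per mother.

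**The concern.** Twins have the same mother, the same delivery circumstances and always the same arm. When correlated observations fall in the same arm, each adds less information than an independent one. A model-based Wald test credits them with full information.

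The error has a known direction. With positive residual correlation within pairs, the reported standard error is too small. This affects the confirmatory comparison and the regression analyses of newborn secondary outcomes, infant carriage and infant growth. Planned power is 82%, so a primary p-value close to 0.05 is quite possible, and that is where a small understatement could change the stated conclusion.

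**Working it through.** **1. Unit of analysis.** The SAP does not name it. Three features point to the newborn: the primary endpoint is an event in a neonate (section 3.4), the covariates are measured on each newborn, and section 8.1 excludes by neonate. If the outcome were counted once per mother, a mother of twins would have two birthweights and two Apgar scores, and the SAP has no rule for choosing between them.

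**2. The plan's own power figure.** Inputs from Table 6: The Gambia, sepsis 1.9%, mortality 0.7%, 31% of deaths due to sepsis, 3500 per arm; Burkina Faso, 1.8%, 0.7%, 17%, 2500 per arm; RR 0.70 for sepsis and 0.75 for mortality; z = 1.96.

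- Control rate = 2 × incidence / (1 + RR); AZI rate = RR × control rate.
- Combined = sepsis + mortality × (1 − proportion of deaths due to sepsis).
- The Gambia, control: 2 × 1.9% / 1.7 = 2.235%; 2 × 0.7% / 1.75 = 0.8%; combined 2.235% + 0.8% × 0.69 = 2.787%. AZI: 1.565% + 0.6% × 0.69 = 1.979%.
- Burkina Faso, control: 2.118% + 0.8% × 0.83 = 2.782%. AZI: 1.482% + 0.6% × 0.83 = 1.980%.
- Weighted 3500:2500, this is 2.785% against 1.979%. With 6000 per arm, power is 0.825 (0.817 from the rounded 2.8% and 2.0%). The stated 0.82 reproduces.

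**3. Effect of twins on the primary test.** All three inputs are assumptions, because the SAP gives none of them: share of newborns who are twins, f = 2-4%; twin-to-singleton risk ratio, k = 1-3; within-pair correlation, ρ = 0.1-0.5.

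- Share of events from twins: s = fk / (fk + 1 − f).
- Design effect: DE = 1 + sρ.
- Correct SE / model-based SE = √DE.
- True type I error = 2 × [1 − Φ(1.96 / √DE)].

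| f | k | ρ | s | DE | SE ratio | Type I error |
|---|---|---|---|---|---|---|
| 2% | 1 | 0.1 | 0.020 | 1.002 | 1.001 | 0.0502 |
| 2% | 3 | 0.3 | 0.058 | 1.017 | 1.009 | 0.0520 |
| 4% | 1 | 0.5 | 0.040 | 1.020 | 1.010 | 0.0523 |
| 4% | 3 | 0.3 | 0.111 | 1.033 | 1.017 | 0.0538 |
| 4% | 3 | 0.5 | 0.111 | 1.056 | 1.027 | 0.0564 |

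In the last row, a reported p-value between 0.044 and 0.05 would cease to be significant once the SE is corrected: 2 × [1 − Φ(1.96 × 1.027)] = 0.044.

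**4. Simulation check.** Null simulations used 12,000 mothers, 4000 replicates and no covariates (Monte Carlo SE about 0.0035). With 2% twin deliveries (2 × 0.02 / 1.02 = 3.9% of newborns), equal risk and ρ = 0.3, type I error was 0.055 for both the naive and the mother-clustered test. With 2% twin deliveries, k = 3 and ρ = 0.5, it was 0.053 naive and 0.048 clustered. Differences this small are hard to separate from simulation noise at these settings. With 4% twin deliveries (7.7% of newborns, above the range in step 3), k = 3 and ρ = 0.5, it was 0.067 against 0.052, which confirms the direction.

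**5. Growth z-scores.** With t the proportion of twin deliveries, DE = 1 + ρ × 2t / (1 + t). For t = 1-4% and ρ = 0.3-0.7 (both assumed), DE runs from 1 + 0.3 × 0.0198 = 1.006 to 1 + 0.7 × 0.0769 = 1.054. The correct SE is 0.3-2.7% larger and type I error is 0.051-0.056.

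**The case against.** The SAP never says that twins enter as separate independent rows. The cohort is defined by dyad or triad, Table 6 counts 6000 per arm to match 12,000 women, and section 7 refers to dummy tables and a CONSORT diagram that are not shown and might fix the denominators. This stands in part: the newborn unit is an inference. But the SAP states no alternative, and a per-mother analysis would leave its covariates undefined for twins.

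The size rests wholly on assumed values, and adjustment for birthweight and Apgar score should absorb some of the within-pair correlation. This also stands, so the range above probably leans high. Nothing in the SAP shows that adjustment removes the correlation entirely.

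Stronger readings are tempting, but the document does not support them:

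- **Maternal outcomes double counted.** Because section 8.1 carries the same model to the secondary outcomes, a reader might infer that a mother of twins contributes two rows to a maternal outcome. Section 4.4 defines maternal sepsis, malaria and the other maternal outcomes on the mother, and nothing says that she is entered twice. Which newborn's covariates a maternal model would use is a separate question.
- **Every newborn secondary outcome has an understated standard error.** Sepsis aetiologies (section 8.1), infant carriage below 4% prevalence (section 8.2) and safety comparisons (section 9) use Fisher's exact test and have no Wald p-value. They too assume independence, but a clustered variance cannot repair them.
- **The power statement is wrong.** It reproduces on its own inputs. It counts women, and the extra newborns from twin births offset part of the design effect.

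**Conclusion.** The point holds as a small, anti-conservative weakness in the specified inference. The unit of analysis is left to inference, and on the natural reading the primary logistic model, and the logistic and linear models for other newborn and infant outcomes, ignore correlation between twins.

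Under the stated assumptions, and before covariate adjustment, standard errors for the primary comparison are understated by about 0.1-2.7% and type I error is about 0.050-0.056 instead of 0.050. The direction requires only positive residual within-pair correlation. The size depends on a twin rate, a risk ratio and a correlation that the SAP does not give. The issue would affect the conclusion only if the primary p-value fell just below 0.05, or if twins supplied a larger share of events than assumed here.

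**What to change.** In sections 6.2 and 8, state that the newborn (or infant) is the unit of analysis for newborn and infant outcomes. Specify standard errors clustered on mother in every regression model of those outcomes in the primary, carriage and anthropometric cohorts; GEE with mother as the cluster is an acceptable alternative. Clustering the variance of the existing logistic model leaves the odds ratio unchanged.

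Where Fisher's exact test is used on newborn outcomes, either report the number of twin pairs by arm beside the result, or count one outcome per mother, and say in advance which.

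The cost is one option in the model command, one or two sentences in the SAP and marginally wider intervals. The sample size need not change.

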## 4 Study Methods

### 4.1 General Study Design and Plan

(ICH E3; 9)

PregnAnZI-2 was a phase III, double-blinded, placebo-controlled randomized clinical trial in which women in labour were randomized to either a single 2g dose of oral AZI or placebo. The study recruited 12,000 women (6750 in The Gambia and 5250 in Burkina Faso).

In The Gambia, women were recruited in two health facilities—Bundung Maternal and Child Health Hospital and Serrekunda Health Centre. In Burkina Faso, recruitment took place in a number of health facilities in Nanoro and Yako health districts.

Women were consented during the antenatal care visits but the study number (randomisation number) was only assigned after screening during labour, provided the woman met the necessary inclusion and exclusion criteria for participation.

Before March 23rd 2020, women and their newborns were visited at 28 day (either at home or at the health facility). After March 23rd 2020, women were not visited at home because of the risk of SARS-CoV-2 transmission, instead the day 28 interview was conducted by telephone. Cases of maternal and neonatal sepsis were identified through passive case detection at the study health facilities during the 28-day follow up period.

Additional scheduled visits at 6 and 12 months were performed for the first 2,000 women recruited (half in The Gambia and half in Burkina Faso) to assess infant anthropometrical measurements, hospitalization and all-cause mortality.

Carriage samples (recto-vaginal swabs, NPS, OPS, rectal swabs and breast milk samples) were collected from 500 randomly selected mother-newborn dyads (or triads in the case of twins). The samples were collected at day 0, day 6, day 28 and at 4 months.

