### 4.4 Study Variables

(ICH E3; 9.5.1. ICH E9; 2.2.2)

The study activities for all mother–newborn dyads/triads enrolled in the study are summarised in the table below (Table 1). In the subset enrolled in the carriage sub–study (n=250 per country), additional home visits were conducted at day 6 and 4 months, and in the subset enrolled in the anthropometrical sub–study (n=1,000 per country) additional home visits were conducted at 6 and 12 months. Surveillance for deaths, sepsis and adverse events was up to day 28 for all participants. In addition, for participants in the carriage sub–study, surveillance for deaths and serious adverse events extended to 4 months, and for participants in the anthropometric sub–study surveillance extended to 12 months.

Note that day 0 is the date of birth rather than date of randomisation as in the study protocol. We have chosen to re–define follow up time as time from birth rather than time from randomisation to ensure that the definition of neonatal sepsis—one of the components of the primary outcome—is consistent with the standard definition.

**Table 1** Summary of study activities

	Pregnancy	Day 0  or Day -1 or Day 1	Day 28 (±4days)
Sensitisation & consent	X		
Health facility visit for delivery		X	
Review of inclusion & exclusion criteria		X	
Randomisation & treatment		X	
Discharge review		X	
Active follow–up (home visit)			X
Passive surveillance 		—————→	

Day 0 is defined to be the day of birth. Note that randomisation and discharge might not occur on the same day as the delivery.

Passive surveillance for adverse events, mortality and sepsis. The surveillance period extends to 4 months for mothers and children participating in the carriage sub–study and to 12 months for children participating in the anthropometrical sub–study.

**Table 2** Carriage samples collected from mother–newborn pairs (n=500; 250/country) enrolled in the carriage sub–study

	Day 0  (or Day –1)	Day 6 (±2 days)	Day 28 (±4 days)	4 Months (±2 weeks)
Mother				
Recto–Vaginal	X 			
Nasopharyngeal	X 	X		
Oropharyngeal	X 	X		
Breast milk		X	X	X
Newborn				
Nasopharyngeal	X 	X	X	X
Oropharyngeal	X 	X	X	X
Rectal	X 	X	X	X

Samples collected on the day of birth (baby) or randomisation (mother) were collected at the health facility. Note that randomisation often occurred the day before delivery.  

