#### Carriage cohort

The cohort will include all mother–newborn dyads/triads who meet the following criteria:

- Selected to be in the carriage cohort
- Included in the primary analysis cohort
- Contributed swabs at day 0 and day 6 (but not necessarily at day 28 or 4 months)
- All members of the dyad/triad alive and participating in the study at the time of the 4–month visit

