## 9 Safety Analyses

We will report the numbers of severe adverse, hospitalisations and deaths in mothers and neonates in the Primary cohort and number of deaths in the Carriage and Anthropometric cohorts. When calculating the incidence, each subject will be counted only once and any repetitions will be ignored; the denominator will be the total population size. P-values will be calculated using Fisher's exact test.

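### Safety is reported only in a cohort that requires every member's day-28 status to be known, so events recorded in excluded dyads and triads go uncounted and Carriage-cohort deaths are zero by construction

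*SAP*

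**What the plan says.** The Primary analysis cohort (SAP Section 6.2) takes in randomised dyads and triads where day-28 "survival status is known for all members of the dyad/triad". Those whose status cannot be determined, "or who have withdrawn from the study, will be excluded from the cohort".

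Section 9 reports severe adverse events, "hospitalisations and deaths in mothers and neonates in the Primary cohort and number of deaths in the Carriage and Anthropometric cohorts". No other safety population is defined. Both smaller cohorts sit inside the Primary cohort: each lists "Included in the primary analysis cohort" among its criteria. The Carriage cohort adds "All members of the dyad/triad alive and participating in the study" at the 4-month visit. The Anthropometric cohort admits infants alive and participating at day 28.

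Surveillance was wider than this. Section 4.4 states: "Surveillance for deaths, sepsis and adverse events was up to day 28 for all participants". For carriage sub-study participants, "surveillance for deaths and serious adverse events extended to 4 months". Section 4.1 says "Cases of maternal and neonatal sepsis were identified through passive case detection at the study health facilities". The safety endpoints in Section 3.4 carry no condition on day-28 status.

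**The concern.** The entry rule suits an analysis of day-28 mortality but not a safety analysis. A safety event on record stays a safety event even if the participant, or another member of the same dyad, is later lost. The rule has three consequences:

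- **Safety.** Events recorded in excluded units fall outside every table that Section 9 describes. The Carriage death count carries no information up to 4 months, and a printed zero in both arms could be read as reassurance.
- **Whole-unit exclusion.** A mother's recorded hospitalisation or death is dropped because her newborn cannot be traced, and a twin's death because the co-twin cannot.
- **Primary outcome.** A newborn with recorded sepsis has already met the composite endpoint, yet is removed if later lost or withdrawn. The SAP describes no all-randomised sensitivity analysis. Section 6.4 (no missing outcomes recorded in the Primary cohort) and Section 8.1 (no censoring for mortality) do not bring these events back.

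**Working it through.** **Safety: which deaths Section 9 can count.** This part follows from the definitions and needs no arithmetic.

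| Recorded event | Primary cohort | Carriage cohort | Anthropometric cohort |
|---|---|---|---|
| Death by day 28, all members' status known | counted | excluded by the survival criterion | excluded by the survival criterion |
| Death by day 28, another member's status unknown or unit withdrawn | not counted | not counted | not counted |
| Infant death after day 28 and before 4 months, carriage sub-study | beyond day 28 | excluded by the survival criterion | only if the infant is also in this cohort |
| Maternal death in the same window | beyond day 28 | excluded by the survival criterion | infants only |

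Carriage-cohort deaths up to the 4-month visit are therefore 0 in both arms, whatever happens in the trial.

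**Primary outcome: the SAP's own figure first.** Inputs from Table 6 are sepsis 1.9% and 1.8%, mortality 0.7% in both countries, share of deaths due to sepsis 31% and 17%, risk ratios 0.70 and 0.75, and 3500 and 2500 per arm. Control rate = 2 × pooled rate / (1 + RR). Composite = sepsis + mortality × (1 − share).

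- The Gambia: control 2.235% + 0.8% × 0.69 = 2.787%; azithromycin 1.979%.
- Burkina Faso: control 2.118% + 0.8% × 0.83 = 2.782%; azithromycin 1.980%.
- Weighted: 2.785% v 1.979%, about 286 events in 12,000. Power at 6000 per arm is 0.825, which reproduces the stated 82%.
- OR = (0.01979/0.98021)/(0.02785/0.97215) = 0.705, 95% CI 0.556 to 0.894.

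**Assumed loss.** The SAP gives no loss rate for the current design; 8% was the allowance in the original one (Section 5). I take 2%, 5% and 8%. Pooled sepsis is (7000 × 1.9% + 5000 × 1.8%)/12,000 = 1.858%, or 223 cases, counting one newborn per dyad.

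| | 2% | 5% | 8% |
|---|---|---|---|
| Dyads excluded (of 12,000) | 240 | 600 | 960 |
| Expected sepsis cases among them (× 1.858%) | 4.5 | 11.2 | 17.8 |
| Same, at three times the incidence | 13.4 | 33.5 | 53.5 |
| Power, risk difference | 0.817 | 0.805 | 0.793 |
| Power, log odds ratio (0.821 with no loss) | 0.81 | 0.80 | 0.79 |

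**Bias.** Let non-events be lost at rate k and events at 3k.

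- Both arms alike: the factor cancels and the OR stays 0.705.
- Azithromycin arm only: 0.705 × (1 − 3k)/(1 − k) = 0.676 / 0.631 / 0.582.
- Control arm only: 0.705 × (1 − k)/(1 − 3k) = 0.735 / 0.788 / 0.853.

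**Tipping point.** Take the planned result, with lost controls at 2.785%, and use a Wald interval on the log odds ratio. The upper limit reaches 1.00 at an OR of 0.794. That requires 17.1 of 120, 20.6 of 300 or 24.2 of 480 excluded azithromycin newborns to have an event: 14.2%, 6.9% or 5.0%, against 2.0% planned.

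**The case against.** **The term Carriage cohort may mean everyone selected.** Section 3.4 uses it for 500 mothers and their children, and on that meaning deaths would not be zero. But Section 6.2 defines the cohort for analysis, Section 6.4 relies on that definition when it cites baseline carriage data as an inclusion criterion, and Section 4.4 calls the selected group the sub-study. If the selected group was meant, Section 9 has to say so. It does stand that deaths up to day 28 in carriage dyads that qualify for the Primary cohort are counted there.

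**The sepsis counts overstate what can be recovered.** This stands. They include cases arising after contact is lost, which no population definition can restore. If half precede loss, the first row of cases falls to about 2 / 6 / 9.

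**Inclusion is fixed before the code is broken, and the trial is double-blind.** Both guard against exclusions steered by arm. Neither restores an omitted event.

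**Partial knowledge within a dyad should be uncommon.** One day-28 contact covers mother and newborn, and earlier death records are accepted. This is plausible and limits the whole-unit problem, but it does not touch withdrawals or the Carriage criterion.

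**Two phrases could be read more loosely.** The exclusion sentence might mean that no member's status is known, but the sentence before it requires status to be known for all. The safety denominator, given as the total population size, might mean all randomised, but the events are still counted in the Primary cohort.

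**Some material is not shown.** The dummy tables and CONSORT diagram might account for excluded units, and use of data recorded before withdrawal depends on consent. Nothing is claimed about either.

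**Conclusion.** The point holds and should be fixed. Followed as written, Section 9 leaves out every safety event recorded in an excluded dyad or triad. It reports a Carriage death count that cannot be other than zero up to the 4-month visit. It also misses carriage sub-study deaths between day 28 and 4 months unless the infant is in the Anthropometric cohort too. None of this depends on whether the losses cause bias. The number of omitted safety events cannot be derived from the SAP.

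The primary-outcome part is minor. Under the assumed losses the power cost is at most about three percentage points. The odds ratio is biased only if the relation between loss and outcome differs by arm, and the SAP gives no sign that it does. The loss rates and the threefold ratio are illustrations, not bounds.

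**What to change.** Before unblinding:

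1. In Section 6.2, define eligibility by newborn for neonatal outcomes and by mother for maternal outcomes, without requiring the status of other members.
2. In Section 9, report safety in all randomised women and their newborns by randomised arm, using all data recorded up to loss or withdrawal as consent allows. If some women did not take the study pills, report it also in those who did. Count sub-study deaths among all participants selected for that sub-study.
3. Add one sensitivity analysis of the primary outcome in all newborns of randomised women, counting every recorded qualifying event. Treat newborns lost without an event first as event-free, then by multiple imputation within arm, with a tipping-point table. Report the odds ratio from the planned logistic model.

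Sepsis recorded before loss should return only through step 3. Adding just those cases to the completers would make inclusion depend on the outcome.

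The cost is SAP wording, one analysis of existing data, and different denominators for mothers and newborns. Treating lost newborns as event-free can itself shift the estimate. With assumed loss of 10% in control and 6% in azithromycin, and half of the events among those lost recorded, the rates become 2.785% × 0.95 and 1.979% × 0.97 and the OR moves from 0.705 to 0.720. With the losses reversed it is 0.690. The imputation and tipping-point steps are there for that reason.
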